#### 4.5. Exploratory Endpoints Analysis

Other exploratory (prespecified/nonprespecified in the protocol) endpoints except for endpoints specified below will use the efficacy estimand and will be summarized by treatment and nominal visit. Unless otherwise specified, missing data will not be explicitly imputed, and assessments are not subject to the type 1 error rate control. Some parameters may be log transformed, if necessary.

The endpoint specified below will be analyzed using both treatment regimen and efficacy estimand similar to primary analysis specified in Section 4.3:

- percent change from baseline in body weight.

**Table 3. Exploratory Efficacy Analyses Not Controlled for Type I Error**

Objective	Relative to the Efficacy Measure	Analysis Conducted in a Manner Similar to Section	Additional Information
Exploratory Objectives			
To assess the clinical effect of tirzepatide compared to dulaglutide at Week 40	Change from baseline in lipid parameters (Total-Cholesterol, HDL-C, LDL-C, VLDL-C, TG)	MMRM model in Section 4.4.2.1	Use corresponding baseline lipid parameters as a covariate.
	Change in daily average 7-point self-monitored blood glucose profiles	ANCOVA model in Section 4.4.2.1	Use baseline SMBG parameter as a covariate.
	Change in IWQOL-Lite-CT (Total, Physical, and Psychosocial) from baseline	ANCOVA model in Section 4.4.2.1	Use baseline IWQOL-Lite-CT (Total, Physical, and Psychosocial) as a covariate.
	Change in Impact of Weight on Self Perception (IW-SP)	ANCOVA model in Section 4.4.2.1	Use baseline IW-SP score as a covariate.
	Change in ability to Perform Physical Activities of Daily Living (APPADL) from baseline	ANCOVA model in Section 4.4.2.1	Use baseline APPADL score as a covariate.
	EIDTQc at Week 40	ANCOVA model in Section 4.4.2.1	None
	Change in GIEH-1 week recall value from baseline	ANCOVA model in Section 4.4.2.1	Use baseline GIEH-1 week recall value as a covariate.
	GIEH-1 since study start recall value at Week 40	ANCOVA model in Section 4.4.2.1	None

Abbreviations: ANCOVA = analysis of covariance; EIDTQc = Emotional Impact of Diabetes Treatment Questionnaire - Comparison; GIEH = Global Impression of Emotional Health; HDL-C = high-density lipoprotein cholesterol; IWQOL-Lite-CT = Impact of Weight on Quality of Life-Clinical Trials Version; LDL-C = low-density lipoprotein cholesterol; MMRM = mixed-effects model for repeated measures; SMBG = self-monitoring of blood glucose; TG = triglyceride; VLDL-C = very-low-density lipoprotein cholesterol.

Note: Exploratory efficacy analyses are not controlled for type I error.

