Visit interval tolerance (days)			±3	±7	±3	±3	±3	±3	±3	±3	±7	±7	—	±7	
Fasting visit			X	X	X	X	X	X	X	X	X	X	X		
Remind participants about 7-point SMBG		X									X				Remind participant to monitor 7-point SMBG profiles (prior to and 2 hrs after the 3 main meals and at bedtime) on 2 nonconsecutive days during the 2 weeks preceding the specified visits.
Review 7-point SMBG values collected in the diary			X									X			
Review hypoglycemic events collected in the diary			X	X	X	X	X	X	X	X	X	X	X	X	
Participant Diary (Electronic)															
Participant diary dispensed		X													eDiary includes SMBG values, collection of intervention administration information on dosing days, and hypoglycemia.
Diary compliance check			X	X	X	X	X	X	X	X	X	X	X	X	
Diary return												X	X		

Study I8F-MC-GPIH	Period I - Screening		Period II- Treatment Period											Period III- Post-treatment Follow-up	Comments
			1	2	3	4	5	6	7	8	9	10	11	ED	
Visits														801	ED = early discontinuation
Weeks from randomization	-3	-2	0	4	8	12	16	20	24	32	40	—	—	4 weeks after the last dose	
Visit interval tolerance (days)			±3	±7	±3	±3	±3	±3	±3	±3	±7	±7	—	±7	
Fasting visit			X	X	X	X	X	X	X	X	X	X	X	X	
Patient-Reported Outcomes (Electronic)															
Complete prior to any clinical assessments															
Impact of Weight on Self-Perception (IW-SP)			X										X	X	Complete PROs before any other study procedures if the participant is not adversely affected by the fasting condition or after the participant has sufficiently recovered from the preceding visit procedures. Must be completed on eCOA device.
Ability to Perform Physical Activities of Daily Living (APPADL)			X										X	X	
Impact of Weight on Quality of Life-Lite-Clinical Trials Version (IWQOL-Lite-CT)			X										X	X	
Emotional Impact of Diabetes Treatment Questionnaire – Comparison (EIDTQc)													X	X	
Global Impression of Emotional Health (1 week recall)			X										X	X	
Global Impression of Emotional Health (since study start recall)													X	X	
Laboratory Tests and Sample Collections															
Hematology	X												X	X	
Hemoglobin A1c (HbA1c)	X		X	X	X	X	X	X	X	X	X	X	X	X	
Clinical chemistry	X		X						X		X	X	X	X	
Glucose	X		X	X	X	X	X	X	X	X	X	X	X	X	
Lipid panel			X						X		X	X	X	X	
Serum pregnancy	X														Only for WOCBP and females with a history of tubal ligation. See Section 10.4.

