#### 4.4.2.1. Analysis for Continuous Outcomes

The analysis to make comparisons between treatment groups for additional secondary continuous outcomes relative to the “efficacy” estimand will be conducted similar to the primary efficacy analysis in Section 4.3.2. The MMRM model will be used for endpoints that have repeated measures over time and the ANCOVA model will be implemented to assess for specific time points. The MMRM model will be updated by adding the baseline category for HbA1c ( $\leq 8.5\%$ ,  $> 8.5\%$ ) as a fixed factor in place of baseline HbA1c, and corresponding baseline values as an additional covariate. Missing data will be addressed by the MMRM model, and no explicit imputation methods will be used. The ANCOVA model (Section 4.3.1) will be updated by adding the baseline category for HbA1c ( $\leq 8.5\%$ ,  $> 8.5\%$ ) as a fixed factor in place of baseline HbA1c, and corresponding baseline values (if available) will be used as an additional covariate in the statistical model.

For the analysis of FSG, waist circumference, and BMI using the treatment regimen estimand, the ANCOVA model (Section 4.3.1) will be implemented with baseline category for HbA1c ( $\leq 8.5\%$ ,  $> 8.5\%$ ) as a fixed factor in place of baseline HbA1c as a covariate and baseline values will be used as an additional covariate in the statistical model.

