## 5. Sample Size Determination

Approximately 250 participants will be randomly assigned in a 1:1 ratio to each study arm. This sample size provides at least 90% power to detect a difference between treatment arms at Week 40 irrespective of adherence to treatment, changes in background OAMs or introduction of rescue antihyperglycemic medication. This sample size is based on an assumed treatment difference of 0.58% with a common standard deviation of 1.3%, using a 2-group t-test and a 0.05 two-sided significance level. The treatment difference is based on the following assumptions for the dose distribution for maximum dose or MTD:

- Tirzepatide MTD will be comprised of the following doses:
  - 15 mg dose - 80% of the participants
  - 10 mg dose - 15% of the participants
  - 5 mg dose - 5% of the participants
- Dulaglutide MTD will be comprised of the following doses:
  - 4.5 mg dose - 80% of the participants
  - 3.0 mg dose - 15% of the participants
  - 1.5 mg dose - 5% of the participants

In addition, the planned sample size provides at least 95% power to detect a difference between treatment arms at Week 40 after randomization regardless of changes in background OAM, assuming that participants stay on treatment and do not take rescue antihyperglycemic medication. This sample size is based on a treatment difference of 0.60% with a common standard deviation of 1.1%, using a 2-group t-test and a 0.05 two-sided significance level. The treatment differences are based on the same assumptions stated above for the treatment-regimen estimand with a 15% discontinuation rate.

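### The since-study-start GIEH analysis (and, more weakly, EIDTQc) omits the related 1-week GIEH baseline already collected at Visit 3; the possible precision gain is modest, unquantified and exploratory only

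*SAP*

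**What the plan says.** SAP Table 3 has eight protocol-specified exploratory rows. Six name a baseline covariate. The two that show 'None' are "EIDTQc at Week 40" and "GIEH-1 since study start recall value at Week 40". Both use the ANCOVA of SAP 4.4.2.1, under which "corresponding baseline values (if available) will be used as an additional covariate in the statistical model".

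Neither item has a corresponding baseline. EIDTQc asks for a comparison with the previous medication (Protocol 8.1.2.2.4), and the since-study-start GIEH item asks for overall change since the trial began (Protocol 8.1.2.2.5). What remains in both models, from SAP 4.3.1 and 4.4.2.1, is treatment plus number of OAMs, dulaglutide dose at screening, region and baseline HbA1c category.

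The 1-week-recall GIEH item is collected at baseline and at the endpoint or early discontinuation visit (Protocol 1.3 and 8.1.2.2.5). Table 3 uses its baseline value only for its own change score.

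Three further statements matter for the remedy. The Visit 3 flow in Protocol 4.1.1, repeated in SAP 1.2, lists random assignment before the patient-reported questionnaires. The trial is open-label (Protocol 6.3). The baseline definition in SAP 4.1 accepts the last value on or before the randomization visit and before the first dose.

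**The concern.** The four adjustment terms are stratification factors, and none of them measures emotional health. A rating of change in emotional health probably depends on where the participant started: someone already at the top of the scale has less room to report being much better than someone at the bottom. If so, the baseline 1-week GIEH explains part of the outcome variance, and leaving it out keeps that part in the error term. The sign of the correlation does not matter, since the gain depends on r².

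For EIDTQc the argument is weaker. That questionnaire asks how the current medication has affected the participant emotionally compared with the earlier one, not about general emotional state.

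At stake is the width of the confidence interval for one exploratory comparison, and perhaps two. A covariate named in advance is also more credible than one added after the data are seen.

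**Working it through.** **1. The plan's own figure.** The SAP gives no sample-size figure for these two outcomes, so the HbA1c calculation in SAP 5 is reproduced to obtain a working number per arm. Inputs: "assumed treatment difference of 0.58% with a common standard deviation of 1.3%, using a 2-group t-test and a 0.05 two-sided significance level", 90% power and 15% discontinuation.

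- n per arm = 2 × (1.960 + 1.282)² × 1.3² / 0.58² = 105.6, rounded up to 106; total 212.
- 212 / (1 - 0.15) = 249.4, or 250 with equal arms. This matches the planned 250.
- Power for the treatment-regimen estimand is 94.2% at 125 per arm and 90.1% at 106 (t distribution: 94.0% and 89.9%).

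I take 106 per arm as evaluable for the questionnaires at Week 40. This is an assumption. The ratios in step 2 barely change at 125 per arm.

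**2. Effect of adding the covariate.** With the outcome SD set to 1, the standard error of the treatment difference is sqrt(2/106) = 0.137. A baseline covariate with within-arm correlation r multiplies it by sqrt(1 - r²). The extra parameter takes residual degrees of freedom from 212 - 6 = 206 to 205, a further factor of sqrt(206/205) = 1.0024. Every r below is assumed.

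| r | sqrt(1 - r²) | Fall in SE | Equivalent extra participants, 1/(1 - r²) - 1 | Factor including lost df | Power of a comparison that had 80% (df loss ignored) |
|---|---|---|---|---|---|
| 0 | 1.000 | 0 | 0 | 1.0024 | 80.0% |
| 0.1 | 0.995 | 0.5% | 1.0% | 0.9974 | 80.4% |
| 0.2 | 0.980 | 2.0% | 4.2% | 0.9822 | 81.6% |
| 0.3 | 0.954 | 4.6% | 9.9% | 0.9563 | 83.6% |
| 0.4 | 0.917 | 8.3% | 19.0% | 0.9187 | 86.4% |

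Break-even: 1 - r² = 205/206 gives r² = 0.0049, so r is about 0.07.

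**3. If the baseline is answered after assignment is known.** Suppose that knowledge shifts the baseline answer by s SD between arms, and affects nothing else. Adjustment then adds a bias of r × s. At r = 0.3 and s = 0.2 the bias is 0.06, the adjusted standard error is 0.131, and the root mean squared error is sqrt(0.131² + 0.06²) = 0.144, against 0.137 unadjusted. The gain is lost. At s = 0.1 it is 0.134, still slightly better than unadjusted. Setting r²s² equal to r² × 2/106 gives a break-even of s = 0.137 at any r.

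**4. Missing baselines.** If participants without a baseline were dropped, losing a fraction r² of them would cancel the gain: 4% at r = 0.2 and 9% at r = 0.3.

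**The case against.** The strongest reply is that nothing here is an error. Table 3 applies the rule in SAP 4.4.2.1 consistently, neither item has a baseline of its own, and the estimate is valid without the covariate. That stands: this is an improvement, not a correction of a fault.

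A reader might infer that precision is being given away for nothing. The documents do not support that. They give no correlation for either item, the gain is nil or slightly negative near r = 0, and the listed Visit 3 order does not guarantee a pre-assignment baseline. Some wording points the other way: the questionnaire step is described as preceding other study procedures, and the Schedule of Activities puts questionnaires before clinical assessments. Neither says that they precede randomization. This objection stands as a condition on the fix. It is not peculiar to this proposal, because the same visit supplies the IWQOL-Lite-CT, IW-SP, APPADL and 1-week GIEH baselines that the SAP already uses as covariates.

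A reader might also infer that the present model leaves chance baseline imbalance as a source of bias. It does not: under randomization the confidence interval already allows for such imbalance.

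Finally, SAP 4.1 permits additional exploratory analyses without amending the SAP, so an adjusted version could be run later. That is true, but a prespecified covariate carries more weight.

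**Conclusion.** The point holds as a low-priority suggestion. For the since-study-start GIEH row, a related baseline is collected and left unused. Adding it would cut the standard error by roughly 0.5% to 8% for an assumed r between 0.1 and 0.4, at a cost of about 0.2% if there is no correlation. The range rests wholly on assumed correlations, and the benefit requires that the baseline be answered before assignment is known. For EIDTQc the same covariate is optional; treating the two items as equally strong cases goes beyond the documents. Both rows are exploratory, without type I error control and without a power target. No primary, key secondary or additional secondary result changes.

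**What to change.** - **SAP Table 3, since-study-start GIEH row:** replace 'None' with 'Use baseline GIEH 1-week recall value as a covariate'. The same edit to the EIDTQc row is optional. While editing, remove the '-1' from the row label, which belongs to the 1-week item.
- **Protocol 4.1.1 and SAP 1.2:** reorder the Visit 3 steps so that the baseline questionnaires are completed before treatment assignment is known, and say so explicitly. This protects every questionnaire baseline, not only this one.
- **SAP 4.5:** state that a missing baseline 1-week GIEH value is filled with the overall mean, ignoring arm, so that no participant is dropped. A sentence is needed because that section otherwise rules out explicit imputation.

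The cost is one or two table cells, one sentence on missing baselines and a reordered list in each document. No new data are collected, and the model loses one degree of freedom.

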#### 4.5.1. Exploratory Analyses Not Specified in the Protocol

**Table 4. Nonprotocol-Specified Exploratory Efficacy Analyses Not Controlled for Type I Error**

Objective	Relative to the Efficacy Measure	Analysis Conducted in a Manner Similar to Section	Additional Information
To assess the clinical effect of tirzepatide compared to dulaglutide at Week 40	Percent change from baseline in body weight	ANCOVA model in Section 4.4.1.1 for treatment regimen estimand and MMRM model in Section 4.4.1.1 for efficacy estimand	None
	Proportion of patients who achieved composite endpoint (“HbA1c <5.7% & Weight Loss $\geq$ 15% & No-Hypo”), defined as 
 
• HbA1c <5.7%
 
• weight loss <math>\geq</math>15%, and
 
• no hypoglycemia, defined as BG <54 mg/dL (<3.0 mmol/L) and/or severe hypoglycemia
 
	Logistic model specified in Section 4.4.2.2	None

Abbreviations: ANCOVA = analysis of covariance; BG = blood glucose; HbA1c = hemoglobin A1c; No-Hypo = No Hypoglycemia.

#### 4.6. Safety Analyses

Safety assessments will be done using the SS (See Section 3) irrespective of adherence to study intervention or initiation of rescue antihyperglycemic medication or prohibited medication, unless indicated otherwise. AEs will be coded from the actual term using the Medical Dictionary for Regulatory Activities (MedDRA) and reported with Preferred Terms (PTs) and System Organ Class (SOC). Selected notable AEs of interest may be reported using High-Level Terms (HLTs) or Standardized MedDRA Queries (SMQs). Summary statistics will be provided for incidence of treatment-emergent AEs (TEAEs), serious AEs (SAEs), and study discontinuation due to AEs, study intervention discontinuation due to AEs, or deaths from the time of first dose through the end of safety follow-up. Counts and proportions of participants experiencing AEs will be reported for each treatment group, and Fisher’s exact test will be used to compare the treatment groups.

Where necessary, for selected continuous safety parameters, the mean change from baseline at Week 40 will be assessed via MMRM using REML. Data from scheduled visits will be utilized for this analysis unless specified otherwise. The model for the analysis during the 40-week treatment period will include treatment, visit, treatment-by-visit interaction, number of background OAMs (0 to 1, 2 to 3), dulaglutide dose at screening, and region as fixed effects, and baseline value of the safety parameter as a covariate. To model the covariance structure within participants, the unstructured covariance matrix will be used. If this model fails to converge, the covariance structures specified in Section [4.3.2](#) will be tested in order until met convergence. If the data does not warrant the MMRM model, then ANCOVA model will be conducted. Where

necessary, the rate of events will be analyzed using a generalized linear MMRM assuming the number of events follow a negative binomial distribution and with treatment as a fixed effect.

#### 4.6.1. Adverse Events

AEs will be coded from the actual term using MedDRA and reported with PTs and SOC.

A TEAE is defined as medical occurrence that emerges during a defined treatment period, having been absent pretreatment, or worsens relative to the pretreatment state, and does not necessarily have to have a causal relationship with this treatment. The maximum severity for each Low-Level Term (LLT) during the baseline period including ongoing medical history will be used as baseline severity. Events with a missing severity during the baseline period will be treated as mild in severity for determining treatment emergence. Events with a missing severity during the postbaseline period will be treated as severe, and treatment emergence will be determined by comparing to baseline severity.

The percentages of patients with TEAEs will be summarized by treatment using MedDRA PT nested within SOC, and Fisher's exact test will be used to compare the treatment groups at both the SOC and PT levels. Events will be ordered by decreasing frequency within SOC. For events that are sex-specific, the denominator and computation of the percentage will include only patients from the given sex.

Overview of the number and percentage of patient who experienced a TEAE, SAE, death, discontinued from study treatment or study due to an AE, and relationship to study drug, will be summarized by treatment.

The percentages of patients with TEAEs, overall and common (common TEAEs occurred in  $\geq 5\%$  of patients before rounding), will be summarized by treatment using MedDRA PT. Events will be ordered by decreasing frequency.

The percentages of patients with TEAEs by maximum severity will be summarized by treatment using MedDRA PT. For each patient and TEAE, the maximum severity for the MedDRA PT is the maximum postbaseline severity observed from all associated LLTs mapping to the MedDRA PT. The maximum severity will be determined based on the nonmissing severities. If all severities are missing for the defined postbaseline period of interest, it will show as missing in the table. Only counts and percentages will be included for the TEAEs by maximum severity.

Patient narratives will be provided for all patients who experience any of the following “notable” events:

- deaths
- SAEs
- pregnancy, and
- permanent discontinuations of study treatment due to AEs.

#### **4.6.1.1. Deaths**

A listing of all deaths will be provided. The listing will include patient identification (ID) including the treatment, site number, date of death, age at the time of enrollment, gender, MedDRA PT of associated AE, time from first dose of study drug to death, time from last dose of study drug to death (if patient had discontinued study drug), cause of death as reported by investigator, cause of death as adjudicated by Clinical Endpoint Committee.

#### **4.6.1.2. Serious Adverse Events**

The number and percentage of patients who experienced an SAE (including deaths and SAEs temporally associated or preceding deaths) will be summarized by treatment using MedDRA PT nested within SOC. Events will be ordered by decreasing frequency within SOC. A listing of all SAEs will be provided. Listing will include but not limited to treatment, patient ID including the site number, treatment group, date of event, age at the time of enrollment, gender, MedDRA SOC and PT, severity, action taken, outcome, relationship to study drug, time from first dose of study drug to the event, and event duration.

#### **4.6.1.3. Discontinuation from Study Due to Adverse Event**

The number and percentage of patients who prematurely discontinue the study due to an adverse event (AE) will be summarized by treatment using MedDRA PT nested within SOC. Events will be ordered by decreasing frequency within SOC. A listing of all the discontinuation from study due to AE will be provided.

#### **4.6.1.4. Discontinuation from Study Treatment Due to Adverse Event**

The number and percentage of patients who prematurely discontinue study drug due to an AE will be summarized by treatment using MedDRA PT nested within SOC. Events will be ordered by decreasing frequency within SOC. A listing of all the discontinuation from study treatment due to AE will be provided.

### **4.6.2. Special Safety Topics**

#### **4.6.2.1. Hypoglycemic Events**

Definitions of different categories of hypoglycemic events are mentioned below.

##### **Level 1**

###### ***Glucose <70 mg/dL (<3.9 mmol/L) and ≥54 mg/dL (≥3.0 mmol/L)***

Level 1 hypoglycemia can alert a person to take action such as treatment with fast-acting carbohydrates. Providers should continue to counsel participants to treat hypoglycemia at this glucose alert value.

**Level 2*****Glucose <54 mg/dL (<3.0 mmol/L)***

Level 2 hypoglycemia is also referred to as documented or BG-confirmed hypoglycemia with glucose <54 mg/dL (<3.0 mmol/L). This glucose threshold is clinically relevant regardless of the presence or absence of symptoms of hypoglycemia.

**Level 3 Severe**

A severe hypoglycemic event is characterized by altered mental or physical status requiring assistance of another person to actively administer carbohydrate, glucagon, or other resuscitative actions for the treatment of hypoglycemia.

The determination of an episode of severe hypoglycemia is made by the investigator based on the medical need of the participant to have required assistance and is not predicated on the report of a participant simply having received assistance.

Examples of severe hypoglycemia in adults are

- altered mental status and the inability to assist in their own care
- semiconscious or unconscious, or
- coma with or without seizures.

**Severe hypoglycemia:** A severe hypoglycemic event is characterized by altered mental or physical status requiring assistance of another person to actively administer carbohydrate, glucagon, or other resuscitative actions for the treatment of hypoglycemia.

**Nocturnal hypoglycemia:** Nocturnal hypoglycemia is a hypoglycemia event, including severe hypoglycemia, which **occurs at night** and presumably during sleep.

To avoid duplicate reporting, all consecutive BG values occurring within a 1-hour period may be considered to be a single hypoglycemic event and the one with the lowest BG value can be selected to be the representative. If two records with the same lowest values within a hour, the earlier occurrence will be selected.

Statistical summaries and analyses will exclude hypoglycemic events occurring after initiation of a new antihyperglycemic therapy. For severe hypoglycemia and level 2 hypoglycemia incidence as well as rate per patient year of exposure will be provided by treatment at specified time intervals. The incidence of hypoglycemic event will be analyzed using logistic regression with treatment, number of background OAMs (0 to 1, 2 to 3), dulaglutide dose at screening, baseline HbA1c category ( $\leq 8.5\%$ ,  $> 8.5\%$ ), and region as fixed effects. The rate of hypoglycemic episodes per patient year may be analyzed using a generalized linear MMRM assuming the number of hypoglycemic episodes follows a negative binomial distribution with the mean modeled using region, number of background OAMs (0 to 1, 2 to 3), dulaglutide dose at screening, baseline HbA1c category ( $\leq 8.5\%$ ,  $> 8.5\%$ ), and treatment as fixed effects if data warrants. The logarithm of years in specified time interval will be adjusted as an offset to account for possible unequal

treatment duration in the specified time interval between patients. When the number of hypoglycemic events is less than 10, the listing of hypoglycemic events will be provided instead.

